2.7.3 Handling of missing values/censoring/discontinuations

PFS and DOR will be censored at the date of the last adequate tumor assessment if no PFS event is observed prior to the analysis cut-off date or before the start of the new anticancer therapy date, whichever is earlier.

The date of last adequate tumor assessment is the date of the last tumor assessment with overall lesion response of CR, PR or SD before an event or a censoring reason occurred. In this case the last tumor evaluation date at that assessment will be used. If no post-baseline assessments

are available (before an event or a censoring reason occurred) then the date of randomization will be used.

In particular, PFS and DOR will be censored at the last adequate tumor assessment if one of the following occurs: absence of event; the event occurred after a new anticancer therapy is administered; the event occurred after two or more missing tumor assessments. The term “missing adequate tumor assessment” is defined as a TA not performed or tumor assessment with overall lesion response of “UNK”. The rule to determine number of missing TAs is based on the time interval between the date of last adequate tumor assessment and the date of an event. If the interval is greater than twice the protocol-specified interval between the TAs and 2 times the protocol-allowed time window around assessments, then the number of missing assessments will be 2 or more.

[figure not shown]
Refer to [Table 2-12](#) for censoring and event date options and outcomes for PFS and DOR.

[figure not shown]
Table 2-10 Outcome and event/censor dates for PFS/DOR analysis

Situation	Date	Outcome
No baseline assessment	Date of randomization	Censored
Progression or death at or before next scheduled assessment	Date of progression (or death)	Progressed
Progression or death after exactly one missing assessment	Date of progression (or death)	Progressed
Progression or death after two or more missing assessments	Date of last adequate assessment prior to missed assessment	Censored
No progression (or death)	Date of last adequate assessment	Censored
Treatment discontinuation due to ‘Disease progression’ without documented progression, i.e. clinical progression based on investigator claim	Date of last adequate assessment	Censored
New anticancer therapy given prior to protocol defined progression	Date of last adequate assessment on or prior to starting new anti-cancer therapy	Censored
Death before first PD assessment	Date of death	Progressed

For Overall Survival, if a subject is not known to have died at the time of analysis cut-off, then OS will be censored at the date of last known date subject was alive, i.e., last contact date (see [Section 2.1](#)).

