If a participant is known to have a contraindication to CT intravenous (IV) contrast media or develops a contraindication during the trial, a non-contrast CT of the chest (MRI is not recommended due to respiratory artifacts, however if CT is not feasible per local regulations, MRI can be performed instead) plus a contrast-enhanced MRI (if possible) of the abdomen and pelvis should be performed.

A whole body bone scan should be performed per institutional standard of care (e.g., Tc-99 bone scan, whole body bone MRI, Fluorodeoxyglucose positron emission tomography (FDG-PET) or sodium fluoride (NaF) PET). Localized CT, MRI or X-rays should be acquired for all skeletal lesions identified on the screening whole body bone scan, which are not visible on the chest, abdomen and pelvis CT/MRI.

If clinically indicated, CT or MRI of other areas (e.g., neck) of disease as appropriate should be performed.

Any potentially measurable lesion that has been previously treated with radiotherapy should be considered as a non-measurable lesion. However, if a lesion previously treated with radiotherapy has clearly progressed since the radiotherapy, it can be considered as a measurable lesion.

Chest x-rays and ultrasound should not be used to measure tumor lesions.

Post-baseline imaging assessments

Imaging assessments as described in Table 8-2 should be performed using the same imaging modality used at baseline, irrespective of study treatment interruption or actual dosing (see Table 8-1). Imaging assessments for response evaluation will be performed every 6 weeks (+/- 7 days) during the first 9 months, and every 12 weeks (+/- 7 days) thereafter as outlined below. Imaging assessments should be scheduled using the randomization date as the reference

date (not the date of the previous tumor assessment), and should be respected regardless of whether treatment with study treatment is temporarily withheld or unscheduled assessments performed.

Additional imaging assessments may be performed at any time during the study at the investigator's discretion to support the efficacy evaluations for a participant, as necessary. Clinical suspicion of disease progression at any time requires a physical examination and imaging assessments to be performed promptly rather than waiting for the next scheduled imaging assessment.

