The date of last administration of study treatment is derived as the last date when a nonzero dose of any component of study treatment was administered as per ‘Study treatment – LAG525/PDR001/carboplatin’ eCRF pages. (Example: if the last spartalizumab dose is administered on 15-Apr-2018, and the last dose of LAG525 is administered on 17-Apr-2018, then the date of last administration of study treatment is on 17-Apr-2018).

Study day

The study day, describes the day of the event or assessment date, relative to the reference start date.

The study day is defined as:

- The date of the event (visit date, onset date of an event, assessment date etc.) – reference start date + 1 if event is on or after the reference start date;
- The date of the event (visit date, onset date of an event, assessment date etc.) – reference start date if event precedes the reference start date.

The reference start date for safety assessments (e.g. adverse event onset, laboratory abnormality occurrence, vital sign measurement, dose interruption, ECOG performance status, PK etc.) is the start of study treatment.

The reference start date for all other, non-safety assessments (i.e., tumor assessment, survival time, disease progression, tumor response) is the date of randomization.

The study day will be displayed in the data listings. If an event starts before the reference start date, the study day displayed on the listing will be negative.

Note: Some measurements may belong to safety measurement and to efficacy measurement (‘death’ is an efficacy endpoint, but it can also be included in the safety analysis). For safety, the ‘study day’ will be calculated relative to start of study treatment, while for efficacy overall survival will be derived relative to randomization date.

Time unit

A year length is defined as 365.25 days. A month length is 30.4375 days (365.25/12). If duration is reported in months, duration in days will be divided by 30.4375. If duration is reported in years, duration in days will be divided by 365.25.

Baseline

For efficacy evaluations, the last non-missing assessment, including unscheduled assessments on or before the date of randomization is taken as “baseline” value or “baseline” assessment.

For safety evaluations, the last available assessment on or before the date of start of study treatment is taken for “baseline” assessment.

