If the time interval between the last adequate tumor assessment (TA) date and the earliest of the following dates is smaller or equal to interval of 2 missing tumor assessments:

1. Analysis cut-off date,
2. Start date of further anti-neoplastic therapy,
3. Date of consent withdrawal,
4. Visit date of study treatment discontinuation or end of post-treatment follow-up discontinuation due to lost to follow-up.

Then the PFS censoring reason will be:

1. 'Ongoing',
2. 'New cancer therapy added',
3. 'Withdrew consent',
4. 'Lost to follow-up',

If the time interval is larger than the interval of 2 missing tumor assessments with no event observed. then the PFS censoring reason will always default to 'Adequate assessment no longer available'. If the time interval between the last adequate tumor assessment date and the PFS event date is larger than the interval of 2 missing tumor assessments then the subject will be censored and the censoring reason will be 'Event documented after two or more missing tumor assessments'.

These summaries on censoring reasons will be produced for PFS by investigators' assessment. The censoring patterns will be compared between treatment arms.

As a supportive analysis, the same type of analysis will be done for PFS, without censoring the data of tumor assessments after the start a the new anticancer therapy.

Clinical benefit rate

CBR based on RECIST 1.1 will be calculated based on the FAS and according to the ITT principle. CBR and its two-sided exact binomial 95% confidence interval [[Clopper and Pearson 1934](#)] will be presented by treatment group.

Overall Survival

OS will be analyzed in the FAS population according to the treatment group assigned at randomization and including all data observed up to the cut-off date. The survival distribution of OS will be estimated using the Kaplan-Meier method. The medians of OS and 95% confidence intervals of the medians [[Brookmeyer and Crowley 1982](#)], along with the proportion of subjects alive at 3, 6, 12 and 18 months and the associated 95% confidence intervals, will be presented for each treatment group.

Censoring pattern of OS

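### The PFS and DOR rule for two or more missing scans rests on one scan interval, but the protocol interval changes from 6 to 12 weeks at 9 months, and every simple reading misclassifies some pattern across the change

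*SAP*

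**What the plan says.** Protocol 8.3.1 sets imaging "every 6 weeks (+/- 7 days) during the first 9 months, and every 12 weeks (+/- 7 days) thereafter". The dates are anchored to randomization rather than to the previous scan: "Imaging assessments should be scheduled using the randomization date as the reference".

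SAP 2.7.3 censors PFS and DOR at the last adequate assessment when "the event occurred after two or more missing tumor assessments". An assessment with an unknown overall response counts as missing. Missing scans are not counted against the schedule but by the time elapsed up to the event: "The rule to determine number of missing TAs is based on the time interval between the date of last adequate tumor assessment". The limit is given only in words: "If the interval is greater than twice the protocol-specified interval between the TAs and 2 times the protocol-allowed time window around assessments", in which case two or more scans are taken as missing.

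SAP Table 2-10 fixes the intended outcomes. "Progression or death after exactly one missing assessment" is an event on its own date. After two or more missing assessments, the participant is censored at the last adequate assessment.

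SAP 2.7.2 uses the same idea for the censoring reasons. It tests whether the time from the last adequate scan to "the PFS event date is larger than the interval of 2 missing tumor assessments", again without a number of weeks.

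**The concern.** A rule based on elapsed time recovers the number of missed scans only if the spacing is constant. Here it doubles at 9 months. A gap of a given length can then mean one missed scan or two, depending on where it starts, and Table 2-10 requires opposite outcomes for those two cases.

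Participants whose gaps span the change are those with long PFS or durable responses. They carry the tails of the Kaplan-Meier curves and the 12- and 18-month event-free proportions planned in SAP 2.7.2. A wrong call turns an event at about week 48 or 60 into censoring at week 30 or 36, or turns censoring at week 24 into an event at week 48. It also assigns the wrong censoring reason, and SAP 2.7.2 plans to compare censoring patterns between arms.

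The change falls within observed follow-up. Protocol Amendment 3 (28-Mar-2019) reports 19 + 21 + 21 = 61 randomized, and the primary cut-off was 27-Feb-2020, 48 weeks later. Those 61 had passed 9 months since randomization by the cut-off, if still followed.

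**Working it through.** **Inputs**
- Interval of 6 then 12 weeks, window 1 week, anchored to randomization: Protocol 8.3.1.
- Month length 30.4375 days: SAP 2.1.1. Nine months = 9 x 30.4375 / 7 = 39.1 weeks.
- Planned weeks 6, 12, 18, 24, 30, 36, then 48, 60, 72 and so on. The step from 36 to 48 is an assumption, because the protocol gives no week numbers.
- For size only: median PFS 3.1 months, quoted for first-line carboplatin in Protocol 1.1.3.4; 34 participants in each of Arms 2 and 3 (Protocol, Amendment 4); each scan missed independently with probability 10% to 20% (assumed).

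The documents state no limit in weeks, so there is no figure to reproduce.

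**Step 1: limits.** Limit = 2 x interval + 2 x window, reading the SAP's conjunction as a sum.
- 6-week interval: 2 x 6 + 2 x 1 = 14 weeks.
- 12-week interval: 2 x 12 + 2 x 1 = 26 weeks.

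**Step 2: patterns across the change.** Errors are in bold.

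| Last adequate scan | Missed | PD | Gap (weeks) | Table 2-10 | Fixed 6 | Fixed 12 | Interval at last scan | Interval at event |
|---|---|---|---|---|---|---|---|---|
| 30 | 36 | 48 | 18 | event | **censored** | event | **censored** | event |
| 36 | 48 | 60 | 24 | event | **censored** | event | event* | event |
| 24 | 30, 36 | 48 | 24 | censored | censored | **event** | censored | **event** |

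*If week 36 is treated as already on the 12-week interval, because its next scan is 12 weeks away. If the interval is judged by date (36 < 39.1), the limit is 14 weeks and this row fails too.

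Rows 2 and 3 have the same 24-week gap and need opposite outcomes. If the last 6-weekly scan is placed at week 42 instead, the same errors occur 6 weeks later. Gaps across the change with no missed scan, or with three, are classified correctly under every reading.

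**Step 3: away from the change.** The two interval-in-force readings are correct. The fixed values are not. The 6-week value censors after one missed 12-weekly scan (week 48 to 72: 24 > 14). The 12-week value counts an event after two or three missed 6-weekly scans (week 12 to 30: 18 <= 26; week 12 to 36: 24 <= 26).

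**Step 4: schedule-based limit.** Limit = planned time from the last adequate scan to the second planned scan after it, plus 2 weeks.
- Last adequate scan at week 24 or earlier: 12 + 2 = 14 weeks.
- Week 30: (48 - 30) + 2 = 20 weeks.
- Week 36 or later: 24 + 2 = 26 weeks.

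This was tested over 9 starting scans, 0 to 2 missed scans, and each of the two scans one week early, on time or one week late: 9 x 3 x 9 = 243 combinations. Wrong calls: fixed 6 weeks 45, fixed 12 weeks 36, schedule-based 0.

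**Step 5: size across the change.** Exponential PFS was simulated with the inputs above. Expected number per arm = 34 x share of progressions whose gap spans week 39.1 x share of those misclassified.

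| Reading | 10% missed | 20% missed |
|---|---|---|
| Fixed 6 weeks | 34 x 0.084 x 0.236 = 0.67 | 34 x 0.098 x 0.320 = 1.07 |
| Fixed 12 weeks | 34 x 0.084 x 0.021 = 0.06 | 34 x 0.098 x 0.053 = 0.18 |
| Interval at last scan (week 36 on 12 weeks) | about 0.3 to 0.4 | about 0.6 |
| Interval at event | 0.06 | 0.18 |

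Including the errors of Step 3, the fixed values misclassify about 3% to 5% (6 weeks) and 2% to 6% (12 weeks) of all progressions under the same assumptions.

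**Step 6: shift per affected participant.** 48 - 30 = 18 weeks; 60 - 36 = 24 weeks; 48 - 24 = 24 weeks.

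**The case against.** The strongest reply is that the SAP does not fix one number for the whole study. A programmer could naturally use the interval in force, which repairs most patterns. With the interval at the last scan, only week 30 to 48 fails (provided week 36 counts as 12-weekly). With the interval at the event, only week 24 to 48 fails. That is right, and it removes all errors away from the change. It does not remove the problem: each of these readings still leaves one ordinary pattern that contradicts Table 2-10, and the SAP names none of them.

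Second, the effect is small and no decision depends on it. PFS and DOR are secondary and summarized by Kaplan-Meier without a test. DOR curves are shown only if there are enough responses. Median PFS is little exposed if most events precede 9 months. All of this stands.

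Third, the fix comes late. The primary efficacy analysis has been run, no arm met the efficacy criteria, and SAP section 1 describes the amendment as preceding a close-out report on safety and PK. This also stands, although SAP 2.15 still sends additional DoR data to the final analysis. A change in censoring now is post hoc and has to be shown as such.

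A reader might also infer that about one participant per arm was misclassified. That size fits the fixed 6-week reading, or the interval at the last scan judged strictly by date. The missed-scan rate has no support in the documents, and the 3.1-month median belongs to single-agent carboplatin.

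**Conclusion.** The point holds. The elapsed-time rule in SAP 2.7.3, and its counterpart in 2.7.2, cannot reproduce Table 2-10 across the change of schedule under any simple reading. The direction of error depends on the reading: the 6-week value and the interval at the last scan censor too often, while the 12-week value and the interval at the event censor too seldom.

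The expected size is about 0.1 to 1 misclassified progression per arm of 34 across the change, each moved by 18 to 24 weeks. This rests on exponential PFS with a 3.1-month median, independent misses of 10% to 20%, and scans at week 36 then week 48. A larger share among responders is plausible for DOR but was not calculated.

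Two stronger inferences are not supported. The documents do not show that the reported PFS or DOR results are wrong, because they do not say which value was programmed or how many scans were missed. Nor is the trial's conclusion in doubt: ORR and the posterior criteria do not use this rule.

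**What to change.** In SAP 2.7.3, define two or more missing assessments by the planned scan weeks from randomization. Censor an event only if the time from the last adequate scan exceeds the planned time to the second planned scan after it, plus 2 weeks. With scans at week 36 then week 48, the limits are:
- 14 weeks if the last adequate scan is at week 24 or earlier;
- 20 weeks if it is at week 30;
- 26 weeks if it is at week 36 or later.

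List the planned weeks explicitly, so that the first 12-weekly scan is not left to interpretation. Use the same limits for the PFS censoring reasons in SAP 2.7.2.

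Because the primary analysis has been run, also state which value was programmed, and list each PFS or DOR event whose classification changes, with its old and new date and status. If none changes, one sentence saying so is enough. If any does, give the affected estimates both ways and label the revision post hoc.

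The cost is a few lines of SAP text and programming, plus a rerun of the PFS and DOR outputs if anything changes. No new data are needed.

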16.3.3.2.10 Sensitivity analyses

This section outlines the possible event and censoring dates for progression, as well as addresses the issues of missing tumor assessments during the study. For instance, if one or more assessment visits are missed prior to the progression event, to what date should the progression

event be assigned? And should progression event be ignored if it occurred after a long period of a patient being lost to follow-up? It is important that the protocol and RAP specify the primary analysis in detail with respect to the definition of event and censoring dates and also include a description of one or more sensitivity analyses to be performed.

Based on definitions outlined in Section 16.3.3.2.7, and using the draft FDA guideline on endpoints (Clinical Trial Endpoints for the Approval of Cancer Drugs and Biologics April 2005) as a reference, the following analyses can be considered:

Table 16-6 Options for event dates used in PFS, TTP, duration of response

Situation		Options for end-date (progression or censoring) ¹ (1) = default unless specified differently in the protocol or RAP	Outcome
Α	No baseline assessment	(1) Date of randomization/start of treatment ³	Censored
В	Progression at or before next scheduled assessment	(1) Date of progression (2) Date of next scheduled assessment ²	Progressed Progressed
C1	Progression or death after exactly one missing assessment	 (1) Date of progression (or death) (2) Date of next scheduled assessment² 	Progressed Progressed
C2	Progression or death after two or more missing assessments	 (1) Date of last adequate assessment² (2) Date of next scheduled assessment² (3) Date of progression (or death) 	Censored Progressed Progressed
D	No progression	(1) Date of last adequate assessment	Censored
E	Treatment discontinuation due to 'Disease progression' without documented progression, i.e. clinical progression based on investigator claim	(1) Ignore clinical progression and follow situations above (2) Date of discontinuation (visit date at which clinical progression was determined)	As per above situations Progressed
F	New anticancer therapy given	Ignore the new anticancer therapy and follow situations above (ITT approach) Date of last adequate assessment prior to new anticancer therapy (3) Date of secondary anti-cancer therapy (4) Date of secondary anti-cancer therapy	As per above situations Censored Censored Event

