G	Deaths due to reason other than deterioration of 'Study indication'	(1) Date of last adequate assessment	Censored (only TTP and duration of response)

¹ =Definitions can be found in Section 16.3.3.2.7.

The primary analysis and the sensitivity analyses must be specified in the protocol. Clearly define if and why options (1) are not used for situations C, E and (if applicable) F.

Situations C (C1 and C2): Progression or death after one or more missing assessments: The primary analysis is usually using options (1) for situations C1 and C2, i.e.

• (C1) taking the actual progression or death date, in the case of only one missing assessment.

² =After the last adequate tumor assessment. "Date of next scheduled assessment" is defined in Section 16.3.3.2.7.

³ =The rare exception to this is if the patient dies no later than the time of the second scheduled assessment as defined in the protocol in which case this is a PFS event at the date of death.

• (C2) censoring at the date of the last adequate assessment, in the case of two or more consecutive missing assessments.

In the case of two or missing assessments (situation C2), option (3) may be considered jointly with option (1) in situation C1 as sensitivity analysis. A variant of this sensitivity analysis consists of backdating the date of event to the next scheduled assessment as proposed with option (2) in situations C1 and C2.

Situation E: Treatment discontinuation due to 'Disease progression' without documented progression: By default, option (1) is used for situation E as patients without documented PD should be followed for progression after discontinuation of treatment. However, option (2) may be used as sensitivity analysis. If progression is claimed based on clinical deterioration instead of tumor assessment by e.g. CT-scan, option (2) may be used for indications with high early progression rate or difficulties to assess the tumor due to clinical deterioration.

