3.2 Power for analysis of key secondary variables

Not applicable.

4 Change to protocol specified analyses

Not applicable.

5 Appendix

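### The clinical-progression row of SAP Table 2-10 does not say what happens when RECIST progression or death follows; read literally, it would drop PFS and DOR events that the protocol default counts

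*SAP*

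**What the plan says.** **SAP 2.7.3, Table 2-10** (cited in the text as Table 2-12) sets event and censoring dates for PFS and DOR. One row covers stopping treatment for disease progression "without documented progression, i.e. clinical progression based on investigator claim". Its date is the last adequate assessment and its outcome is censored. Another row, "Progression or death at or before next scheduled assessment", gives an event on the actual date. A further row censors participants with no progression or death at the last adequate assessment. No order of precedence is stated.

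**Protocol Appendix 3, Table 16-6, situation E** carries the same label and offers two options. Option (1) is "Ignore clinical progression and follow situations above". Option (2) counts progression at the discontinuation visit. Section 16.3.3.2.10 then says: "By default, option (1) is used for situation E as patients without documented PD should be followed for progression after discontinuation of treatment".

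Option (1) is the "default unless specified differently in the protocol or RAP", so the analysis plan may depart from it. The same section attaches a condition: "Clearly define if and why options (1) are not used for situations C, E and (if applicable) F".

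**SAP Section 4**, "Change to protocol specified analyses", is answered as not applicable.

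**The concern.** The SAP outcome matches neither protocol option. It does not send the participant back to the other rows, and it does not score an event at discontinuation.

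Participants stopped for clinical progression are expected to progress or die soon. Appendix 3 (16.3.4.4) reserves this stop reason for documented deterioration of symptoms that points to progression. Removing them at the previous scan would therefore be informative censoring, and the Kaplan-Meier curve would sit too high. For DOR the same applies to confirmed responders whose response ends in RECIST progression or death due to the underlying cancer.

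The later events were meant to be seen. Protocol 8.3.1 keeps scans going after a stop without RECIST progression; they became optional only with amendment 4 (February 2021), after the primary cut-off of 27 February 2020. The supportive PFS analysis in SAP 2.7.2 lifts only the new-therapy censoring, so it would not show the effect of this row.

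**Working it through.** **Step 1. Compare the rules for one participant.** The participant stops for clinical progression, starts no new therapy, and has RECIST progression or dies by the next scheduled scan.

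| Source | Outcome |
|---|---|
| Protocol Table 16-6, E option (1) | Event on the later date |
| Protocol 12.5.1 (PFS) | Event; the only censoring triggers are cut-off and new therapy |
| SAP 2.7.1, PFS definition | Event; clinical deterioration is not itself an event, but is not made a censoring time |
| SAP 2.7.3, prose triggers | Event; the triggers are no event, event after new therapy, event after two or more missing assessments |
| SAP Table 2-10, event-by-next-scan row | Event |
| SAP Table 2-10, clinical-progression row, read literally | Censored at the previous scan |

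The PFS censoring reasons in SAP 2.7.2 have no category that fits the last line. If this participant dies before any post-baseline scan, the table's last row gives an event at death. The clinical-progression row, with the 2.7.3 fallback, gives censoring at randomization.

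**Step 2. Find where the rules differ.** With no later event, both documents censor at the last adequate assessment. With new therapy first, or two missed assessments first, both also censor. They differ only when RECIST progression or death (for DOR, cancer death) comes before either of those.

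**Step 3. Illustrate the size.** Neither document states a PFS target or an expected share of clinical stops, so there is no planned figure to reproduce. The inputs are:
- median PFS 3.1 months, the carboplatin figure quoted in protocol 1.1.3.4 and used here as an assumption
- scans every 6 weeks (protocol 8.3.1)
- 34 participants, the number randomized to each of Arms 2 and 3 (amendment 4)
- a share f of participants whose event is preceded by a clinical stop, assumed 10% to 30%, with no intervening new therapy

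Hand check, with exponential times, all events detected at scans, and stops unrelated to event time. The median is 3.1 × 4.348 = 13.48 weeks.
- Probability of passing one 6-week interval: r = 0.5^(6/13.48) = 0.7345, so d = 1 − r = 0.2655.
- Protocol default at 6 months (four scans): r⁴ = 0.291.
- Literal row: a fraction f of each interval's events leaves at the preceding scan, so the conditional survival is r/(1 − f·d).
  - f = 10%: (0.7345/0.9735)⁴ = 0.324
  - f = 20%: (0.7345/0.9469)⁴ = 0.362
  - f = 30%: (0.7345/0.9204)⁴ = 0.406

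A simulation of 200,000 participants, with 15% of events as deaths on their exact dates and a cut at 104 weeks, gives:

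| f | Events lost per 34 | 6-month PFS, default → literal | Median (months) |
|---|---|---|---|
| 10% | 3.4 | 0.288 → 0.321 | 4.1 → 4.1 |
| 20% | 6.8 | 0.286 → 0.356 | 4.1 → 4.1 |
| 30% | 10.1 | 0.288 → 0.403 | 4.1 → 4.9 |

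At f = 20%, if half of those who stop start new therapy before the later event, the loss falls to 3.4 events and the shift is 0.319 → 0.357. If all do, both rules give 0.358. With a 5.0-month median and no new therapy, f = 20% moves 6-month PFS from 0.462 to 0.533 and the median from 5.5 to 6.9 months.

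DOR was not simulated.

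**The case against.** The strongest defence is that the row is only a clarification. Someone with later RECIST progression does have documented progression and so belongs in an event row. The row is not tied to the date of stopping, whereas the new-therapy row is tied to the start of that therapy. The event definition, the prose triggers and the censoring reasons all point towards counting the later event. This is a fair account of what the authors probably meant, and it is why the SAP cannot be said to have settled on discarding events.

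It does not remove the problem. Participants with no later event are already censored at the same date by the no-progression row. On the benign reading the clinical-progression row is redundant; it changes a result only where it overrides a later event. The label is the one Table 16-6 uses for a situation that includes later events. A programmer working from the table alone could code it either way.

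Two further points stand. The SAP is allowed to depart from the default, so a departure is not itself an error; what is missing is the stated reason. The share f is also unknown, and protocol 8.3.1, which requires prompt imaging on clinical suspicion, should keep it down.

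**Conclusion.** The clinical-progression row is ambiguous and, read literally, contradicts the rest of the SAP and an undisplaced protocol default. It should be corrected, but the stakes are limited.

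The direction is clear: a literal reading can only remove events, and it raises the curves where those events would otherwise count. The size cannot be determined from the documents. The shift in 6-month PFS from about 29% to 32–40% rests on the assumed 10–30% share, a 3.1-month median and no intervening new therapy. It shrinks as more participants start new therapy first, reaches zero if all do, and may leave the median unchanged.

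Three stronger readings are not supported:
- A reader might infer that the reported PFS and DOR have lost events. The documents do not show which rule was programmed.
- A reader might take the closure of Arm 1, which had more discontinuations for progressive disease, as evidence that this arm is most affected. Nothing says those stops lacked RECIST documentation.
- A reader might extend the doubt to the efficacy decision. ORR and the proof-of-preliminary-efficacy criteria do not use this table. PFS and DOR are secondary and are summarized by arm without a formal test or target.

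**What to change.** Replace the row with: *Clinical progression without documented RECIST PD: ignore the claim and apply the other rows (event at later RECIST PD or death; otherwise censor at last adequate assessment).* For DOR, keep the existing limit to death due to the underlying cancer.

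Then confirm from the analysis programs which rule was used, and re-run PFS and DOR if it was the literal row. If the sponsor wants to keep the literal rule, it should state the reason, list it in SAP Section 4, and add the protocol default as a sensitivity analysis.

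The cost is one row of wording, a check of the programs and, at most, one re-run of two descriptive endpoints. No new data are needed. The PFS and DOR estimates may become somewhat shorter.
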